- b) study day on or after the date of the booster/third dose will be calculated as: date of assessment/event – date of the injection in booster/third dose analysis + 1;

**Study day relative to the most recent injection** will be calculated as below:

- a) study day on or after the date of the first injection in Part 2 open-label phase (if applicable) but before the second injection in Part 2 open-label phase (if applicable) will be calculated as: date of assessment/event – date of the first injection of mRNA-1273 in Part 2 open-label phase + 1;
- b) study day on or after the date of the second injection in Part 2 open-label phase (if applicable) but before the injection in booster dose analysis (if applicable) will be calculated as: date of assessment/event – date of the second injection of mRNA-1273 in Part 2 open-label phase + 1;
- c) study day on or after the date of booster/third dose analysis (if applicable) will be calculated as: date of assessment/event – date of the injection in booster/third dose analysis + 1;  
if study day is on the same day as the injection, date and time will be compared with the injection date and time.

**For calculation regarding antibody values in booster/third dose analysis**, antibody values reported as below LLOQ will be replaced by  $0.5 \times \text{LLOQ}$ . Values that are greater than the upper limit of quantification (ULOQ) will be converted to the ULOQ if actual values are not available, and actual values will be used if available. Missing results will not be imputed.

The following analysis periods for Long-term and booster/third dose phase safety analyses will be used as applicable for specific subjects group in this study:

- Up to 28 days after any vaccination (mRNA-1273 primary series or booster/third dose): this stage starts at the day of each vaccination and continue through the earliest date of (the day of each vaccination and 27 subsequent days, next vaccination [if applicable]). This analysis period will be used as the primary analysis period for safety analyses including unsolicited AE, except for solicited AR, unless specified otherwise.
- Overall period or throughout the study: this analysis period starts at the first injection on Day 1 and continues through the earliest date of (study completion, discontinuation from the study, or death).

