### Long-term Analysis (including Part 2 Open-Label Phase)

For unsolicited AE or assessments that will be collected throughout the study after mRNA-1273 primary series, this analysis period starts from the first dose date of mRNA-1273 and continues until the earliest date of (booster dose, study completion, discontinuation from the study, or death).

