### Booster/Third Dose Analysis

For unsolicited AE or assessments that will be collected throughout the study, this analysis period starts from the booster/third dose date and continues until the earliest date of (study completion, discontinuation from the study, or death).

**Unscheduled visits:** Unscheduled visit measurements will be included in analysis as follows:

- In scheduled visit windows per specified visit windowing rules.
- In the derivation of baseline/last on-treatment measurements.
- In the derivation of maximum/minimum on-treatment values and maximum/minimum change from baseline values for safety analyses.
- In individual subject data listings as appropriate.

**Visit windowing rules:** The analysis visit windows for protocol-defined visits are provided in [Appendix B](#).

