### **Treatment groups:**

The following vaccination groups will be used for summary purposes:

- Long-term Analysis (Part 1 Open-Label Phase plus Part 2 Blinded and Open-Label Phase):
  - mRNA-1273: Participants from mRNA-1273 group in Part 1 open-label phase or Part 2 blinded phase
  - Placebo - mRNA-1273: Participants from Part 2 blinded phase placebo group who cross over and receive mRNA-1273 in Part 2 open-label phase
- Part 3, First Two Doses of Primary Series:
  - mRNA-1273 25 µg: Participants from mRNA-1273 group in Part 3 open-label phase
- Booster/Third Dose Analysis:
  - mRNA-1273 - mRNA-1273 Booster: Participants from the Part 1 open-label phase or Part 2 blinded phase mRNA-1273 group who received a booster dose of mRNA-1273 in Part 1 or Part 2
  - Placebo - mRNA-1273 - mRNA-1273 Booster: Participants from the Part 2 blinded phase placebo group who crossed over to receive mRNA-1273 in Part 2 open-label phase, and received a booster dose of mRNA-1273 in the booster phase
  - mRNA-1273 - mRNA-1273.214 Booster: Participants from the Part 1 open-label phase or Part 2 blinded phase mRNA-1273 group who received a booster dose of mRNA-1273.214 in Part 1 or Part 2
  - Placebo - mRNA-1273 - mRNA-1273.214 Booster: Participants from the Part 2 blinded phase placebo group who crossed over to receive mRNA-1273 in the Part 2 open-label phase, and received a booster dose of mRNA-1273.214 in booster phase
  - mRNA-1273 - mRNA-1273 Third Dose: Participants from the Part 3 open-label phase who received a third dose of mRNA-1273 in Part 3

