### **Analysis periods**

The following analysis periods and treatment groups will be used for long-term and booster dose analysis.

- Long-term Analysis (Part 1 Open-Label Phase plus Part 2 Blinded and Open-Label Phase, until Booster Dose)

| Group               | Category                    | Start Date                      | End Date  |
|---------------------|-----------------------------|---------------------------------|---|
| mRNA-1273           | Safety                      | Date of First Dose of mRNA-1273 | Earliest date of booster dose (exclusive), study discontinuation, study completion, death, or data cutoff |
| Placebo - mRNA-1273 |                             |                                 | Earliest date of booster dose (inclusive), study discontinuation, study completion, death, or data cutoff |
| mRNA-1273           | Efficacy/
Immunogenicity | Date of First Dose of mRNA-1273 | Earliest date of booster dose (inclusive), study discontinuation, study completion, death, or data cutoff |
| Placebo - mRNA-1273 |                             |                                 | Earliest date of booster dose (inclusive), study discontinuation, study completion, death, or data cutoff |

- Long-term analysis (Part 1 Open-Label Phase plus Part 2 Blinded and Open-Label Phase, Regardless of Booster Dose) incidence rate will also be performed for the entire study period after the first dose of mRNA-1273 regardlesss of booster dose.

| Group               | Category                    | Start Date                      | End Date  |
|---------------------|-----------------------------|---------------------------------|---|
| mRNA-1273           | Safety                      | Date of First Dose of mRNA-1273 | Earliest date of study discontinuation, study completion, death, or data cutoff |
| Placebo - mRNA-1273 |                             |                                 | Earliest date of study discontinuation, study completion, death, or data cutoff |
| mRNA-1273           | Efficacy/
Immunogenicity | Date of First Dose of mRNA-1273 | Earliest date of study discontinuation, study completion, death, or data cutoff |
| Placebo - mRNA-1273 |                             |                                 | Earliest date of study discontinuation, study completion, death, or data cutoff |

- Part 3, First Two Doses of Primary Series Analysis

| Group           | Category | Start Date                      | End Date  |

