### **6.3.1. Adverse Events**

A treatment-emergent AE (TEAE) is defined as any event occurring during the study not before exposure to study vaccine or any event already present that worsens after exposure to study vaccine. [Note: worsening of a pre-existing condition after vaccination will be reported as a new AE.]

Adverse events will also be evaluated by the investigator for the coexistence of MAAE which is defined as an AE that leads to an unscheduled visit to a healthcare practitioner.

Unsolicited AEs will be coded by PT and SOC using MedDRA and summarized by age and vaccination group, and stage (up to 28 days after any vaccination, follow-up analysis period and overall stage; see [Section 6.1](#) for definitions of vaccination group and stage).

All summary tables (except for the overall summary of AEs) for unsolicited AEs will be presented by SOC and PT for TEAEs with counts of subjects included. SOC will be displayed in internationally agreed order. PT will be displayed in descending order of frequency of total mRNA-1273 group with all dose level combined in Part 1 and in Part 2 correspondingly and then alphabetically within SOC. When summarizing the number and percentage of subjects with an event, subjects with multiple occurrences of the same AE or a continuing AE will be counted once. Subjects will be presented according to the highest severity (the strongest relationship) in the summaries by severity (of related AEs), if subjects reported multiple events under the same SOC and/or PT.

Percentages will be based upon the number of subjects in the Safety Set for specified analysis (long-term analysis or booster/third dose analysis) within each age and vaccination group.

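### The open-label/booster SAP starts its overall safety stage at Day 1 with no group-specific start, in conflict with its own long-term and booster safety periods

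*SAP*

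**What the plan says.** All places below are in the SAP for the Part 2 open-label phase, booster doses and Part 3 (the open-label/booster SAP), unless the blinded-phase SAP is named.

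- **Section 6.1, safety periods.** The long-term and booster/third-dose safety periods "will be used as applicable for specific subjects group in this study". Two follow: 28 days after any vaccination (the primary safety period) and an overall period. Of the latter it says "Overall period or throughout the study: this analysis period starts at the first injection on Day 1"; it ends at study completion, discontinuation or death.
- **Section 6.1, Long-term Analysis.** For events collected throughout the study, "this analysis period starts from the first dose date of mRNA-1273 and continues until the earliest date of" booster, completion, discontinuation or death.
- **Section 6.1, Booster/Third Dose Analysis.** For the same kind of events, "this analysis period starts from the booster/third dose date and continues until the earliest date of" completion, discontinuation or death.
- **Section 6.1, Treatment groups.** One group is "Placebo - mRNA-1273: Participants from Part 2 blinded phase placebo group who cross over and receive mRNA-1273 in Part 2 open-label phase".
- **Section 6.1, Analysis periods, until-booster table.** As read, safety for the mRNA-1273 group ends at the booster date, exclusive. For Placebo - mRNA-1273 it ends at "Earliest date of booster dose (inclusive), study discontinuation, study completion, death, or data cutoff". In the booster/third-dose table, safety starts on the booster/third-dose date for all groups.
- **Section 3.3.1.** The primary booster and third-dose endpoints for MAAEs, SAEs and AESIs count events after that dose.
- **Section 6.3.1.** Unsolicited adverse events are summarized by age, vaccination group and "stage (up to 28 days after any vaccination, follow-up analysis period and overall stage; see" Section 6.1.

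**The concern.** The same section gives two start dates for the same groups. A crossover child's Day 1 injection was placebo. A boosted child's Day 1 injection was the primary series, or placebo. A programmer who builds the overall stage from Section 6.1 and tabulates it by vaccination group, as Section 6.3.1 directs, would count placebo-time events under vaccine and primary-series events under booster. MAAEs, SAEs and AESIs (including myocarditis/pericarditis and MIS-C) are followed for the whole study, so their attribution rests on these dates.

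There are two smaller problems. Section 6.3.1 refers to Section 6.1 for a follow-up stage that is not defined there. The booster-day cut-off also differs between the two long-term groups, so a booster-day event would appear in two sets of tables for one group and in one set for the other.

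**Working it through.** The SAP states no figure to reproduce. The check sets the definitions side by side and then counts days.

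**1. Start of the whole-study safety period**

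| Group | Overall stage (6.1) | Group-specific text and tables (6.1) |
|---|---|---|
| mRNA-1273, long-term | Day 1 | first mRNA-1273 dose (the same day) |
| Placebo - mRNA-1273, long-term | Day 1 (placebo) | first mRNA-1273 dose |
| Booster and third-dose groups | Day 1 (primary series or placebo) | booster/third-dose date |

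The starts agree for children vaccinated from Day 1 in the long-term analysis and disagree in the other two rows. For the booster and third-dose rows, Section 3.3.1 sides with the group-specific date.

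**2. Can Day 1 mean crossover or booster day?** Section 6.1 has separate names for those days, Crossover Day 1 and BD-Day 1. The overall bullet nearly repeats the one in Section 6.1 of the blinded-phase SAP, where Day 1 is appropriate. The 28-day bullet was adapted to name the primary series and booster/third dose; the overall bullet was not. The follow-up bullet of the blinded-phase SAP was not carried over, although Section 6.3.1 still uses that stage.

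**3. Does the TEAE definition remove the problem?** Not for booster columns, because primary-series events already follow exposure to study vaccine. Nor clearly for the crossover column: the blinded-phase SAP uses the same definition for tables that include a placebo group.

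**4. Size of the added time.** If Day 1 is the first injection, placebo days in the overall stage = crossover day − 1, and pre-booster days = booster day − 1.

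Section 4.4 of the blinded-phase SAP makes Part 2 children under 6 eligible for unblinding from 6 months after Dose 2. With Dose 2 at Day 29 and 6 months taken as 180 days, that is Day 29 + 180 = Day 209, hence 208 placebo days (208/30.4 = 6.8 months). The same section allows for crossover after an authorization, so earlier days are shown too. All crossover days, and a booster 180 days after crossover Dose 2, are illustrative assumptions.

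| Crossover | Placebo days in overall stage | Booster (crossover + 28 + 180) | Pre-booster days in overall stage |
|---|---|---|---|
| Day 57 | 56 | Day 265 | 264 |
| Day 120 | 119 | Day 328 | 327 |
| Day 209 | 208 | Day 417 | 416 |

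For a child vaccinated from Day 1, the 6-month interval for Amendment 7 boosters gives Day 29 + 180 = Day 209, so at least 208 pre-booster days. Appendix J offers mRNA-1273.214 from 3 months after Dose 2: taking 90 days, Day 29 + 90 = Day 119, so at least 118.

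**5. Booster-day boundary.** Let B be the booster day. The booster safety period is B to end of study.

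- Placebo - mRNA-1273 (inclusive): long-term period runs to B. Overlap 1 day, gap 0.
- mRNA-1273 (exclusive): long-term period runs to B − 1. Overlap 0 days, gap 0.

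Comparable safety cut-offs elsewhere are exclusive: unblinding for both groups in Section 6.1 of the blinded-phase SAP, and the third dose in Part 3. Inclusive is the convention of the efficacy/immunogenicity rows. Making the Placebo - mRNA-1273 safety row exclusive gives overlap 0 and gap 0 in both groups.

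**The case against.** The strongest defence is that the overall bullet sits under a sentence limiting the periods to the groups they suit. The correct group-specific starts follow in the text and tables, Section 3.3.1 counts booster events only after the dose, and Section 6.3.1.1 promises separate booster/third-dose tables. On that view a careful programmer would use the right dates. This stands in part: it shows what was probably intended and makes misattribution a risk only. It does not settle the matter, because the qualifier never says which group uses which period, and Section 6.3.1 names the overall stage for tables by vaccination group.

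Three further points stand. The 28-day primary period is defined per vaccination and cut at the next one, so it is untouched. The inclusive/exclusive difference comes from a table read by program, possibly with merged cells, and needs checking against the source; the Day 1 conflict does not depend on it. The long-term analysis regardless of booster overlaps the booster period by design and is no error.

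The time-of-day rule for same-day events does not resolve the boundary. It sets the study day relative to the most recent injection, not the safety period to which an event belongs.

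**Conclusion.** The SAP states a rule for the overall stage that contradicts its own long-term and booster periods and, if followed, gives wrong attribution. It also orders a follow-up stage that it does not define. Both should be corrected. The booster-day mismatch should be corrected too if the source table confirms it.

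The added placebo time depends on when crossover occurs: about 7 months under the scheduled under-6 unblinding, possibly less after an authorization (56 to 208 days in the illustration). The boundary mismatch is one day. It duplicates an event across the long-term and booster tables, not within one table, and only for crossover children with an event on the booster day.

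A reader might infer more, but the documents do not support it:

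- That events will be misassigned. The group-specific periods may well be the ones programmed.
- That 7 months is a minimum for every crossover child. Section 4.4 of the blinded-phase SAP leaves room for earlier crossover.
- That every boosted crossover child is counted twice. The planned maximum of 1,000 placebo recipients per age group is a ceiling on children, not a count of booster-day events.

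**What to change.** - In Section 6.1, give the overall stage a start by group: first mRNA-1273 dose for the long-term groups, booster/third-dose date for the booster and third-dose groups. State which period each group's tables use.
- Check the until-booster table against its source, and make the booster date exclusive for safety in both long-term groups.
- Define the follow-up stage for these analyses (start relative to the last dose of that analysis, end before the next study dose), or remove it from Section 6.3.1.

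The cost is SAP wording and a check of the date derivations. No new data are needed.

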### Long-term Analysis (including Part 2 Open-Label Phase)

For unsolicited AE or assessments that will be collected throughout the study after mRNA-1273 primary series, this analysis period starts from the first dose date of mRNA-1273 and continues until the earliest date of (booster dose, study completion, discontinuation from the study, or death).

### Booster/Third Dose Analysis

For unsolicited AE or assessments that will be collected throughout the study, this analysis period starts from the booster/third dose date and continues until the earliest date of (study completion, discontinuation from the study, or death).

**Unscheduled visits:** Unscheduled visit measurements will be included in analysis as follows:

- In scheduled visit windows per specified visit windowing rules.
- In the derivation of baseline/last on-treatment measurements.
- In the derivation of maximum/minimum on-treatment values and maximum/minimum change from baseline values for safety analyses.
- In individual subject data listings as appropriate.

**Visit windowing rules:** The analysis visit windows for protocol-defined visits are provided in [Appendix B](#).

### **Incomplete/missing data:**

- Imputation rules for missing prior/concomitant medications, non-study vaccinations and procedures are provided in [Appendix C](#).
- Imputation rules for missing AE dates are provided in [Appendix D](#).
- For laboratory assessments, if majority of results are indefinite, imputation of these values will be considered. If the laboratory results are reported as below the LLOQ (e.g., <0.1), the numeric values will be imputed by  $0.5 \times \text{LLOQ}$  in the summary. If the laboratory results are reported as greater than the ULOQ (e.g., “>3000”), the numeric values will be imputed by ULOQ in the summary.
- Other incomplete/missing data will not be imputed, unless specified otherwise.

### **Treatment groups:**

The following vaccination groups will be used for summary purposes:

- Long-term Analysis (Part 1 Open-Label Phase plus Part 2 Blinded and Open-Label Phase):
  - mRNA-1273: Participants from mRNA-1273 group in Part 1 open-label phase or Part 2 blinded phase
  - Placebo - mRNA-1273: Participants from Part 2 blinded phase placebo group who cross over and receive mRNA-1273 in Part 2 open-label phase
- Part 3, First Two Doses of Primary Series:
  - mRNA-1273 25 µg: Participants from mRNA-1273 group in Part 3 open-label phase
- Booster/Third Dose Analysis:
  - mRNA-1273 - mRNA-1273 Booster: Participants from the Part 1 open-label phase or Part 2 blinded phase mRNA-1273 group who received a booster dose of mRNA-1273 in Part 1 or Part 2
  - Placebo - mRNA-1273 - mRNA-1273 Booster: Participants from the Part 2 blinded phase placebo group who crossed over to receive mRNA-1273 in Part 2 open-label phase, and received a booster dose of mRNA-1273 in the booster phase
  - mRNA-1273 - mRNA-1273.214 Booster: Participants from the Part 1 open-label phase or Part 2 blinded phase mRNA-1273 group who received a booster dose of mRNA-1273.214 in Part 1 or Part 2
  - Placebo - mRNA-1273 - mRNA-1273.214 Booster: Participants from the Part 2 blinded phase placebo group who crossed over to receive mRNA-1273 in the Part 2 open-label phase, and received a booster dose of mRNA-1273.214 in booster phase
  - mRNA-1273 - mRNA-1273 Third Dose: Participants from the Part 3 open-label phase who received a third dose of mRNA-1273 in Part 3

### **Analysis periods**

The following analysis periods and treatment groups will be used for long-term and booster dose analysis.

- Long-term Analysis (Part 1 Open-Label Phase plus Part 2 Blinded and Open-Label Phase, until Booster Dose)

| Group               | Category                    | Start Date                      | End Date  |
|---------------------|-----------------------------|---------------------------------|---|
| mRNA-1273           | Safety                      | Date of First Dose of mRNA-1273 | Earliest date of booster dose (exclusive), study discontinuation, study completion, death, or data cutoff |
| Placebo - mRNA-1273 |                             |                                 | Earliest date of booster dose (inclusive), study discontinuation, study completion, death, or data cutoff |
| mRNA-1273           | Efficacy/
Immunogenicity | Date of First Dose of mRNA-1273 | Earliest date of booster dose (inclusive), study discontinuation, study completion, death, or data cutoff |
| Placebo - mRNA-1273 |                             |                                 | Earliest date of booster dose (inclusive), study discontinuation, study completion, death, or data cutoff |

- Long-term analysis (Part 1 Open-Label Phase plus Part 2 Blinded and Open-Label Phase, Regardless of Booster Dose) incidence rate will also be performed for the entire study period after the first dose of mRNA-1273 regardlesss of booster dose.

| Group               | Category                    | Start Date                      | End Date  |
|---------------------|-----------------------------|---------------------------------|---|
| mRNA-1273           | Safety                      | Date of First Dose of mRNA-1273 | Earliest date of study discontinuation, study completion, death, or data cutoff |
| Placebo - mRNA-1273 |                             |                                 | Earliest date of study discontinuation, study completion, death, or data cutoff |
| mRNA-1273           | Efficacy/
Immunogenicity | Date of First Dose of mRNA-1273 | Earliest date of study discontinuation, study completion, death, or data cutoff |
| Placebo - mRNA-1273 |                             |                                 | Earliest date of study discontinuation, study completion, death, or data cutoff |

- Part 3, First Two Doses of Primary Series Analysis

| Group           | Category | Start Date                      | End Date  |
|-----------------|----------|---------------------------------|---|
| mRNA-1273 25 µg | Safety   | Date of First Dose of mRNA-1273 | Earliest date of third dose (exclusive), study discontinuation, study completion, death, or data cutoff |

|                 |                |                                 |   |
|-----------------|----------------|---------------------------------|---|
| mRNA-1273 25 µg | Immunogenicity | Date of First Dose of mRNA-1273 | Earliest date of third dose (inclusive), study discontinuation, study completion, death, or data cutoff |
|-----------------|----------------|---------------------------------|---|

- Booster/Third Dose Analysis

| Group                                       | Category                | Start   | End   |
|---|-------------------------|---|---|
| mRNA-1273 - mRNA-1273 Booster               | Safety                  | Date of Booster/Third Dose  | Earliest date of study discontinuation, study completion, death, or data cutoff |
| mRNA-1273 - mRNA-1273 Third Dose            |                         |   |   |
| Placebo - mRNA-1273 - mRNA-1273 Booster     |                         |   |   |
| mRNA-1273 - mRNA-1273.214 Booster           |                         |   |   |
| Placebo - mRNA-1273 - mRNA-1273.214 Booster |                         |   |   |
| mRNA-1273 - mRNA-1273 Booster               | Efficacy/Immunogenicity | Date of Booster/Third Dose (considered as pre-booster/third dose data, exclusive) | Earliest date of study discontinuation, study completion, death, or data cutoff |
| mRNA-1273 - mRNA-1273 Third Dose            |                         |   |   |
| Placebo - mRNA-1273 - mRNA-1273 Booster     |                         |   |   |

For mRNA-1273.214 Booster Dose, only safety analysis related to endpoints in section 3.3.1 will be performed.

For Part 3 mRNA-1273 Third Dose, only safety and immune analysis related to endpoints in section 3.3 will be performed.

